Pentoxifylline (PTX), a methylxanthine-derivative and nonspecific phosphodiesterase inhibitor with combined anti-inflammatory and antifibrogenic properties ⁽¹⁴⁾, can lower the levels of circulating proinflammatory cytokines, such as TNF- α , IL-1 β and IL-6, by means of a cyclic adenosine monophosphate (cAMP)-dependent mechanism ⁽¹⁵⁾. Furthermore, pentoxifylline has been proposed to have antioxidant properties ⁽¹⁵⁾. Moreover, pentoxifylline facilitates synthesis and release of serotonin and inhibits its uptake, suggesting that pentoxifylline enhances serotonergic presynaptic response in the CNS ⁽¹⁶⁾. In addition, it showed antidepressive-like effects in a rat model of acute myocardial infarction ⁽¹⁷⁾.

Aim of the study

The aim of the current study is to evaluate the potential antidepressant effect of pentoxifylline in adult patients with MDD. We hypothesized that MDD patients taking pentoxifylline as adjuvant would present greater amelioration of their depressive symptoms than patients taking placebo. Furthermore, we will assess the relationship between HAM-D score and several peripheral biomarkers as well as their role in diagnosis and therapeutic targets of MDD.

Patients and methods

Eighty adult outpatients who will meet the diagnostic and statistical manual of mental disorder IV (DSM-IV) criteria for major depression will be participated in the trial ⁽¹⁸⁾. Patients will be recruited from the armed psychiatry hospital, Egypt. Patients have a baseline Hamilton Rating Scale for Depression (Ham-D) score of at least 18 ⁽¹⁹⁾. Patients will be allocated in a random fashion: 40 patients will receive escitalopram 20 mg/day plus placebo (Control group) and 40 patients will receive escitalopram 20 mg/day plus pentoxifylline 800 mg/day (400mg bid) (morning and evening). Treatment duration will be 12 weeks. Adherence to the study medication will be assessed by collecting the empty blister packs of the consumed drugs from the patients every 4 weeks. Patients will be assessed by a psychiatrist at baseline, 4, 8, and 12 weeks after starting the medication. Any unexpected risks appeared during the course of the research will be cleared to participants and the ethical committee on time. An informed consent will be obtained from all participants in this research.

Measurements:

1. Full patient history, demographic data and clinical examination.

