2. Patients will be assessed by a psychiatrist at baseline, 4, 8, and 12 weeks after starting the medication. The principal measure of the outcome will be the 17-item Ham-D. Remission is defined as an endpoint Ham-D total score ≤ 7 . Treatment response is defined as at least 50% improvement during the study period in the Ham-D scale. The mean decrease in Ham-D score from baseline will be the main outcome measure of response of depression to treatment (Primary outcome).
3. Questionnaire to evaluate the side effects of the study medications.
4. **Biological markers (Secondary outcome):** Blood sample collection at baseline and after the treatment to evaluate the following:
 - i) Serum level of Brain-derived Neurotrophic Factor (BDNF)
 - ii) Serum Serotonin level
 - iii) Serum levels of the following proinflammatory and anti-inflammatory markers:
 - Tumor necrosis factor-alpha (TNF-a)

- Interlukin-6 (IL-6)
 - Interlukin-10 (IL-10)
- iv) Serum levels of 8-hydroxy-2'-deoxyguanosine (8-OHdG), a biomarker of oxidative damage.

Inclusion criteria:

- 1- Eighty adult outpatients with the Diagnostic and Statistical Manual of Mental Disorders-IV (DSM-IV) diagnosis of MDD based on a MINI Neuropsychiatric Interview (MINI) (American Psychiatric Association., 2000; Sheehan et al., 1998), without psychotic features and a total 17 item HAM-D score of at least 18 with item 1 (depressed mood) scored 2 or greater were eligible.
- 2- Patients were requested to be free of all the psychotropic and anti-inflammatory medications for at least 4 weeks before participating in the study.

Exclusion criteria:

1. Patients with bipolar I or bipolar II disorder
2. Patients with personality disorders
3. Patients with eating disorders
4. Patients with substance dependence or abuse
5. Patients with concurrent active medical condition
6. Patients with history of seizures
7. Patients with history of receiving Electroconvulsive therapy (ECT)
8. Patients with inflammatory disorders
9. Patients with allergy or contraindications to the used medications
10. Patients with finally pregnant or lactating females

Statistical analysis:

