All tests of treatment effect will be conducted by external statistician blind to group allocation, at a two-sided significance level of 0.05, and no adjustments were made for multiple comparisons. Type III sums of squares will be used to adjust for unbalanced data in the interactions of these models of variance. Importantly, general linear model for analysis of covariance (ANCOVA) model will be used for the primary analysis of change from baseline to endpoint in HAM-D total score. The primary analysis was performed using a mixed-effects model repeated measures (MMRM) ANCOVA. As a sensitivity analysis, will be carried out using the last observation carried forward (LOCF) approach in case of dropouts. Furthermore, a two-way repeated measures analysis of variance (ANOVA) for HAM-D score (time–treatment interaction) will be used. The two groups as a between-subjects factor (group) and the four time interval measurements during treatment as the within-subjects factor (time) will be

considered. Moreover, repeated measures ANOVA will be used to test the time x group interaction on the changes in the biomarkers between baseline and week 12 in the two groups. Chi square test was used for the qualitative variables. The statistical analysis was performed with IBM©SPSS® Statistics V 22. Pearson's correlation will be calculated to assess the relationship among variables.

References:

- 4- **Capuron L and Miller AH.** Immune system to brain signaling: neuropsychopharmacological implications. *Pharmacology & Therapeutics*. 2011; 130(2):226-38.

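### The HAM-D/biomarker relationship rests on an unspecified, unadjusted Pearson correlation, which large drug effects on both measures would inflate if the arms are pooled

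*Combined protocol and SAP*

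**What the plan says.** The Aim of the study section of the combined protocol and SAP adds a second objective to the efficacy question: "we will assess the relationship between HAM-D score and several peripheral biomarkers as well as their role in diagnosis and therapeutic targets of MDD". The Statistical analysis section serves that objective with one sentence: "Pearson's correlation will be calculated to assess the relationship among variables". It leaves five things open: the pairs of variables, the visit, level or change, arms together or apart, and any covariates.

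Measurements, item 4, lists six markers as secondary outcomes: BDNF, serotonin, TNF-alpha, IL-6, IL-10 and 8-OHdG. They are measured twice: "Blood sample collection at baseline and after the treatment to evaluate the following". HAM-D is measured four times: "Patients will be assessed by a psychiatrist at baseline, 4, 8, and 12 weeks after starting the medication".

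Arm and time terms do appear in Statistical analysis, but only in the HAM-D models and in the repeated measures ANOVA of each marker. Neither relates a marker to HAM-D. Tests of treatment effect are run "at a two-sided significance level of 0.05, and no adjustments were made for multiple comparisons". No threshold is stated for the correlations themselves.

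**The concern.** The trial's own rationale makes treatment arm a possible common cause of the two quantities to be correlated. The background says that pentoxifylline lowers proinflammatory cytokines, and the hypothesis is that it improves depressive symptoms more than placebo. If both are true, the pentoxifylline arm differs from the control arm on the marker and on HAM-D. A correlation over all 80 patients then mixes this between-arm difference with the patient-level relationship, which is what the aim is about. Randomisation does not remove this, because arm affects both outcomes.

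The artefact is largest when the drug works well on both measures. That is also when a marker is most likely to be put forward as a therapeutic target, so the trial could report support for a mechanism that it had not tested.

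**Working it through.** **Inputs.** From the documents: 40 patients per arm, 80 in total; six markers; two blood samples. Assumed: a two-sided 0.05 test of each r, complete data, normal values and, as the case to test, zero correlation between marker and HAM-D within each arm. The plan gives no effect size, SD or expected correlation, so there is no planned figure to reproduce and the effects are shown as a range.

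**Arms pooled, one value per patient (change score or week-12 value).** With two equal groups, zero within-group correlation and standardised group differences d1 and d2, the pooled correlation is

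r = (d1·d2/4) / √[(1 + d1²/4)(1 + d2²/4)].

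For example, 0.8 and 0.8 give 0.16/1.16 = 0.138, and 1.0 and 1.0 give 0.25/1.25 = 0.200. The critical |r| at n = 80 is 1.991/√(78 + 1.991²) = 0.220. Rejection rates come from 40,000 simulated trials per row:

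| Effect on HAM-D / marker (SD) | Pooled r | Significant, plain Pearson |
|---|---|---|
| 0 / 0 | 0.00 | 4.9% |
| 0.3 / 0.3 | 0.02 | 5.4% |
| 0.5 / 0.5 | 0.06 | 8.2% |
| 0.5 / 0.8 | 0.09 | 12.4% |
| 0.8 / 0.8 | 0.14 | 23.1% |
| 1.0 / 1.0 | 0.20 | 43.6% |
| 1.5 / 1.5 | 0.36 | 93.8% |

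With arm removed first (partial correlation, 77 df), the rate is 4.8% to 5.1% in every row. By Fisher's approximation, the plain test reaches 50% at about 1.07 SD on both measures and 80% at about 1.34 SD.

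**General improvement over 12 weeks, one value per patient.** A shift shared by all patients adds a constant to each variable and drops out of r. Simulation gives r = 0.00 and 4.9% significant.

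**General improvement, baseline and week-12 rows stacked (160 rows).** The same formula applies, with visit in place of arm. The critical |r| is 0.155. Ranges cover within-person correlations of 0 and 0.5 (15,000 simulated trials each):

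| Shift in HAM-D / marker (SD) | r | Significant |
|---|---|---|
| 1 / 0.2 | 0.04 | 8.5% to 9.9% |
| 2 / 0.3 | 0.10 | 25% to 27% |
| 2 / 0.5 | 0.17 | 59% to 60% |
| 2 / 0.8 | 0.26 | 94% to 95% |

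Centring the stacked rows by visit removes the shift. It still rejects about 8% at a within-person correlation of 0.5, because 160 rows from 80 patients are not independent. Correlating within-patient changes keeps the rate at 4.8% to 5.3%.

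**Baseline only.** No study treatment has been given, so neither arm nor time can contribute.

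The arm-adjusted rates were checked with arm as the only covariate. Adjustment for baseline values was not simulated.

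**The case against.** The strongest reply is that silence is not a choice. The plan never says that arms or visits will be pooled. Correlations within each arm, or at baseline only, fit the sentence equally well, and a baseline correlation suits the diagnostic part of the aim. This stands: the defect is that the plan permits an inflated analysis, not that it has selected one.

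A reader might also infer that a false positive is likely whenever the drug works on both measures. The figures do not support that. Inflation is negligible at 0.3 SD, modest at 0.5 SD, and still below one in two at 1.0 SD on both. The drug is also an add-on to escitalopram in both arms, and nothing in the documents indicates effects that large.

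A third inference would be that improvement in all patients biases the correlation in any case. It does so only if visits are stacked, which no section describes.

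Two further limits stand. The available background describes anti-inflammatory, antioxidant and serotonergic actions, but no drug effect on BDNF or IL-10, so the common-cause argument is documented for only some of the six markers. And the 0.05 level is written for tests of treatment effect, so its use for the correlations is an assumption.

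The reply does not close the gap. No other analysis in the plan relates a marker to HAM-D, and a single sentence leaves every one of these options open after the data are seen.

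**Conclusion.** The concern holds in a limited form. The sole stated method for the HAM-D/biomarker aim is unspecified and unadjusted. If post-treatment values or changes are correlated over both arms, the false-positive rate per marker rises from 5% to about 8% at 0.5 SD, 23% at 0.8 SD and 44% at 1.0 SD on both measures. It barely moves at 0.3 SD. These figures rest on assumed effect sizes, 80 complete patients, normal data and no within-arm link. Bias from general improvement is conditional on stacking visits.

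The documents do not support saying that the plan has adopted a pooled analysis or that a spurious finding is to be expected. The aim concerned is secondary, and the primary HAM-D comparison is untouched.

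**What to change.** Replace the correlation sentence in Statistical analysis with text to this effect: for each of the six markers, the association between change in the marker and change in HAM-D from baseline to week 12 will be estimated as a partial correlation adjusted for treatment arm and both baseline values, and will also be shown separately by arm; associations at baseline will use baseline samples only; baseline and week-12 values will not be combined in one correlation.

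In the Aim of the study, label any therapeutic-target reading as hypothesis-generating. With blood taken only at baseline and after treatment, the order of marker change and symptom change cannot be seen, and adjustment for arm does not cure that.

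The change is to wording only, with the same data and software. It costs one degree of freedom per correlation for arm (78 to 77) and three with both baseline values (78 to 75). The reported correlations will tend to be smaller, the by-arm estimates rest on 40 patients each, and the mechanistic claim becomes more modest.

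### The six serum biomarkers are to be compared on change with no baseline covariate and no stated scale; adjusting for baseline, with logs for skewed markers, would recover power from the same samples

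*Combined protocol and SAP*

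**What the plan says.** Measurements, item 4, makes the biological markers the secondary outcome: BDNF, serotonin, TNF-alpha, IL-6, IL-10 and 8-OHdG, all as serum levels. It introduces the cytokines as "Serum levels of the following proinflammatory and anti-inflammatory markers". There are two samples per patient: "Blood sample collection at baseline and after the treatment to evaluate the following".

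Under Statistical analysis, "repeated measures ANOVA will be used to test the time x group interaction on the changes in the biomarkers" between baseline and week 12. For associations, Pearson's "correlation will be calculated to assess the relationship among variables"; the Aim of the study names the relation of HAM-D score to the peripheral biomarkers as an objective. Tests are run "at a two-sided significance level of 0.05, and no adjustments were made for multiple comparisons".

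The section uses ANCOVA for the HAM-D change but names no covariate for the biomarkers. It is silent on transformation, distribution checks, rank-based alternatives and values below the assay limit. The plan does not use the word raw; that scale is inferred, because serum levels and their changes are the only scale it mentions.

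**The concern.** Two separate features of the biomarker test can waste information.

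- **No baseline covariate.** A change score subtracts the whole baseline value, whatever its correlation with the week-12 value. When that correlation is moderate, this adds noise that ANCOVA would remove. It applies on any scale and needs no assumption about skew.
- **No stated scale.** Serum concentrations cannot be negative and may be right-skewed. If they are, and if treatment acts proportionally, a few high values dominate the raw change, and Pearson's coefficient is attenuated and less stable.

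At stake is the trial's evidence on mechanism. With 40 per arm, an effect could be missed that the same samples would show under a better-chosen analysis. The primary HAM-D analysis is not involved.

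**Working it through.** **Inputs from the documents.** 40 per arm, 80 in total (Patients and methods); two-sided 0.05; two sampling times. No SD, CV, distribution, effect size, power or dropout is given for any marker, so there is no figure of the plan's own to reproduce.

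**Assumptions.** Baseline to week-12 correlation ρ = 0.4 to 0.6 on the log scale; log-normal markers with log-SD σ = 0.3, 0.5, 0.7 and 1.0; no dropout. CV = √(exp(σ²) − 1) gives 0.31, 0.53, 0.80 and 1.31.

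**Step 1: what the planned test is.** With two groups and two times, the time × group F-test is the square of the two-sample t-test on change.

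**Step 2: baseline adjustment, on a scale where values are normal.** The variance of the group contrast is proportional to 2σ²(1 − ρ) for change and to σ²(1 − ρ²) for ANCOVA. The ratio of ANCOVA to change is (1 + ρ)/2, that is 0.70 at ρ = 0.4 and 0.80 at ρ = 0.6. Take an effect that ANCOVA detects with 80% power, so that its expected z is 1.960 + 0.842 = 2.802:

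- ρ = 0.4: change score z = 2.802 × √0.70 = 2.344; power = Φ(2.344 − 1.960) = 65%.
- ρ = 0.6: change score z = 2.802 × √0.80 = 2.506; power = Φ(2.506 − 1.960) = 71%.

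So omitting the covariate costs about 9–15 points before scale is considered.

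**Step 3: adding scale, by simulation.** The effect is set so that log-scale ANCOVA has about 80% power: log ratio = 2.802 × σ × √(1 − ρ²) × √(2/40). At σ = 0.3 and ρ = 0.4 this is 2.802 × 0.3 × 0.917 × 0.224 = 0.172, a fall to exp(−0.172) = 0.84 of control. Ranges cover the two correlations and simulation error of one or two points.

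| CV | Planned test (raw change), marker falls | Planned test, marker rises | Raw ANCOVA | Log change | Log ANCOVA |
|---|---|---|---|---|---|
| 0.31 | 58–65% | 65–70% | about 77% | 65–72% | about 80% |
| 0.53 | 51–58% | 61–66% | 72–74% | 65–72% | about 80% |
| 0.80 | 43–48% | 57–59% | about 67% | 65–72% | about 80% |
| 1.31 | 33–35% | 47–51% | 55–57% | 65–72% | about 80% |

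The effect of scale alone is raw change against log change at the same correlation. For a falling marker it is about 6 points at CV 0.31 and 33–35 at CV 1.31. For a rising marker it is about 0 and 15–20. Under no effect, rejection rates stayed between 3.9% and 5.3%.

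**Step 4: correlations, n = 80, log-scale r = 0.31.**

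| CV | Raw Pearson, marker with HAM-D | Raw Pearson, two skewed markers |
|---|---|---|
| 0.31 | 79% | 77% |
| 0.53 | 76% | 71% |
| 0.80 | 73% | 64% |
| 1.31 | 64% | 49% |

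Pearson on logs has 80–81% and Spearman 75–76%. Against HAM-D the raw loss is thus 80 − 79 = 1 to 81 − 73 = 8 points up to CV 0.80. At CV 1.31 the two most extreme of 80 patients carry a median 47% of a marker's sum of squares on the raw scale, against 16% on logs; at CV 0.31 it is 21% against 16%.

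**Step 5: the case least favourable to logs.** With normal markers, an additive effect and CV up to 0.30, log ANCOVA still has 73–80% power, against 67–69% for the planned test. Against raw ANCOVA, however, logs give up about 4–12 points at CV 0.3–0.4.

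**The case against.** The strongest reply is that the premise of skew is not in the documents. They give no distribution for any marker, and being bounded at zero does not make a variable materially skewed. The exclusion of inflammatory disorders, active medical conditions and recent anti-inflammatory drugs may trim the upper tail. The larger CVs in the table, which supply the striking losses, are assumptions. This stands, and it is why the point on scale is conditional. It does not touch the point on baseline adjustment.

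Three stronger readings are tempting, and the documents do not support them.

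- A reader might set 33–35% against 80% and blame the scale for the whole gap. Much of it is change score against ANCOVA: at CV 0.31 and 0.53, raw ANCOVA alone recovers most of it.
- A reader might apply the falling-marker losses to all six markers. The protocol's background says that pentoxifylline lowers TNF-alpha and IL-6 but facilitates serotonin synthesis and release, and it gives no direction for BDNF, IL-10 or 8-OHdG. For a rising marker the loss from scale is much smaller.
- A reader might conclude that logs for every marker are free, or that the plan rules transformation out. Step 5 contradicts the first; the second reads silence as a decision.

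It is also fair to say that the loss is small for the correlations that serve the stated aim, and that Spearman is no more powerful than raw Pearson at CV 0.31–0.53. The larger losses concern correlations between markers.

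**Conclusion.** The point holds as a minor, inexpensive improvement to a secondary analysis. The firm part is baseline adjustment: at CV 0.31 it lifts power from about 58–70% to about 77% without any transformation, given a correlation of 0.4–0.6. The conditional part is the log scale. Its value runs from nothing (a rising marker with mild skew) to about a third of the power scale (a falling marker at CV 1.31), and it turns negative against raw ANCOVA if a marker is near-normal with CV 0.3–0.4. The harm is missed effects and results that lean on a few patients. False positives are not increased by the choice of scale or by the change score, and the HAM-D primary analysis is unaffected. All power figures rest on the assumed correlation, distribution and zero dropout.

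**What to change.** Amend the Statistical analysis section to say:

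1. Each biomarker is compared between groups by ANCOVA of the week-12 level with the baseline level as covariate.
2. Right-skewed markers are analysed on the log scale, with log baseline as covariate, and reported as a ratio of geometric means with 95% CI. Which markers these are is either pre-specified by marker or decided from blinded, pooled baseline data.
3. Correlations are computed on the same scale as the group comparison, with Spearman's coefficient as a check.
4. Values below the assay limit are handled by a stated rule.

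The cost is SAP wording; no patients, samples or assays are added. Logged effects read as ratios rather than differences. If a marker judged skewed is in fact near-normal with CV 0.3–0.4, logs give up about 4–12 points of power against raw ANCOVA, which is why the scale is best settled marker by marker. Settling it before unblinding also avoids a data-driven choice across six unadjusted comparisons.
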